- Aim 1 – Determine oxytocin effects on weight, REE, and body composition: We hypothesize that 8-week intranasal oxytocin compared to placebo (a) reduces body weight, (b) increases REE (adjusted for lean/fat free mass), and (c) reduces total body, visceral, and liver fat in adults with obesity.
- Aim 2 – Determine oxytocin effects on caloric intake and underlying neural pathways (fMRI): We hypothesize that intranasal oxytocin compared to placebo reduces caloric intake at a test meal (independent of weight change), mediated by (a) reduced activation (in fasted and fed states) of reward-related food motivation (VTA, OFC, anterior insula) and homeostatic (hypothalamus) brain regions during a visual food stimuli paradigm and (b) increased impulse control indicated by increased activation (fasted state) of cognitive control-related brain regions (dlPFC, dACC, anterior portion of supplementary motor cortex/preSMA) during a validated task requiring the engagement of cognitive control to suppress impulsive responses.

The study is conducted under an Investigational New Drug application cleared by the U.S. Food and Drug Administration at a single study site, and the institutional review board approved the study protocol.

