2.5.2. Analysis of neuroimaging data

fMRI data will be analyzed using Statistical Parametric Mapping software running under the MATLAB® environment (SPM12) [52]. Preprocessing steps will include realignment and geometric unwarping using magnitude and phase images from the field map, slice-time correction, echo planar (EPI) co-registration to the participant's segmented, skull-stripped, bias-corrected T1-weighted image, normalization to Montreal Neurological Institute space with resampling to 2 mm isotropic using 4th degree B-spline interpolation, and smoothing with a 6 mm isotropic full width at half-maximum Gaussian kernel. Each run of EPI data will be evaluated for motion: (a) the degree of linear movement will be assessed and classified (threshold = 3 mm linear movement in orthogonal planes), and (b) the ART toolbox (Artifact Detection Tools; www.nitrc.org/projects/artifact_detect) will be used to detect outlier volumes based on image intensity relative to the global mean image (threshold = 3.5xSD) and motion (threshold = 0.8 mm, measured as scan-to-scan movement). Individual runs will be excluded if they show either (a) >3 mm linear movement and >10% outliers, or (b) >20% outliers.

For subject-level analyses, a general linear model (GLM) either with regressors of high-calorie foods, low-calorie foods, and objects (food cue paradigm) or with regressors of successful stop trials and failed stop trials (SST) will be specified. Regressors will be placed at the onset of each condition within a block, convolved with the canonical hemodynamic response function. Global mean signal and motion outliers will be entered as nuisance regressors. Following GLM estimation, the primary contrast (high-calorie foods versus objects, successful versus failed stop trials) will be computed at the single-subject level to estimate condition effects at every voxel, separately for each session (fasted/fed). For subsequent group-level analysis, we will use a factorial design with baseline versus 4-week contrasts to examine changes in brain activation

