following oxytocin treatment in a-priori defined regions of interest (ROIs, food cue paradigm: VTA, OFC, anterior insula; SST: dlPFC, dACC, preSMA). For mediation analyses, beta values will be extracted from subject-level contrast images for clusters within a-priori ROIs that meet family-wise error rate correction ($p < 0.05$) using Marsbar software [53]. We will also analyze activation in additional reward-related food motivation and impulse control-related brain regions and the whole brain (applying α -error correction procedures). Moreover, we will examine activation in the hypothalamus as a brain region responsible for energy homeostasis.

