We will conduct regression-based mediation analyses to explore mechanisms underlying the proposed effects of intranasal oxytocin treatment: We will investigate whether (a) the change in brain activation in key reward-related food motivation (VTA, OFC, anterior insula) and homeostatic (hypothalamus) regions during fasted and fed states as well as in cognitive control-related regions (dlPFC, dACC, preSMA) during the fasted state from baseline following 4-week oxytocin treatment mediates change in caloric intake at a test meal 6 weeks from baseline, (b) the change in caloric intake at 6 weeks from baseline mediates the percentage change in body weight at 8 weeks from baseline, and (c) the change in REE at 6 weeks from baseline mediates the percentage change in body weight at 8 weeks from baseline.

Safety and compliance endpoints (assessed at each study time point) will be reported and tested for between-group (oxytocin versus placebo) differences. Endpoints regarding the off-treatment follow-up study time point (week 14 visit) will be reported and analyzed using MMRM in relation to baseline and end of treatment (week 8 visit) time points where appropriate (separately from on-treatment analyses).

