
Abbreviations: BMI, body mass index; EKG, electrocardiogram; ALT, alanine transaminase; AST, aspartate transaminase; MRI, magnetic resonance imaging; DXA, dual-energy X-ray absorptiometry.

Table 2. Study procedures at individual study time points.

Assessments	Screen	BL		ON-T (oxytocin versus placebo)				OFF-T
		BL1	BL2	W2	W4	W6	W8	W14
Screening and safety								
• Medical history and physical exam, MMSE	X	X	X	X	X	X	X	X
• Screening/safety labs (CBC, TSH, urine drug screen (at screen only); CMP, HbA1c)	X		X	X	X		X	X
• EKG	X			X			X	
• M.I.N.I.	X							
• Adverse events monitoring, review of concomitant medication, pregnancy test (urine/serum hCG) in females	X	X	X	X	X	X	X	X
Anthropometric measurements (height, weight, %IBW ^a , BMI ^b , WHR ^c)								
	X	X	X	X	X	X	X	X
Energy expenditure, body composition, and fat metabolism								
• Indirect calorimetry (REE)		X				X	X	
• DXA (total fat mass, lean body mass)		X					X	
• MRI (abdominal and thigh measures)		X					X	
• 1H-MRS (liver fat)		X					X	
• Fat biopsy		X		X				
Caloric intake								
• Breakfast test meal (experimental assessment of caloric intake)		X				X		
• 4-day food record (typical eating)		X	X		X	X	X	X
• 24-hr food recall (caloric intake immediately preceding visit)		X	X		X	X		
Laboratory assessments								
• Blood for metabolic profile (e.g., insulin sensitivity, lipid panel, hsCRP, appetite-regulating hormones), gonadal steroids, leukocyte RNA, DNA (optional)			X	X	X	X	X	X
• 24h urine (e.g., cortisol, creatinine)		X					X	
• Stool (e.g., microbiome; optional)			X		X		X	
• Hair (e.g., cortisol; optional)			X				X	
Neuroimaging								
• Food cue task (fasting and post-meal): VTA, OFC, anterior insula, hypothalamus			X		X			
• Impulse control tasks (Stop-Signal Task; Multi-Source Interference Task [optional]) (fasting): dPFC, dACC, preSMA			X		X			
• Handedness questionnaire		X						
Psychological, behavioral, and quality of life assessments								
• Physical activity (PPAQ ^d)	X				X	X		X
• Appetite (VAS ^e), eating behavior and attitudes (EDEQ ^f , DEBQ ^g , EADES ^h , TFEQ ⁱ)		X	X		X	X	X	X
• Reward-related food motivation (BIS/BAS ^j , CTT ^k , PFS ^l) and reward-related behaviors and choices			X		X			X

(Probabilistic Reward Task and Social Reward Task, TEPS ^m ; optional)					
• Impulse control and compulsivity (Delay Discounting Task, Reversal Learning Task, BIS-11 ⁿ , BOCS ^o , SRS ^p ; optional)		X		X	

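### Brain-mediator values exist only where a cluster survives FWE correction on an unstated group-level term; a region with no cluster, and the hypothalamus, have no extraction rule

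*Combined protocol and SAP*

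**What the plan says.** Section 2.5.2 names the subject-level contrasts: high-calorie foods against objects for the food-cue task, and successful against failed stops for the stop-signal task. They are computed separately for the fasted and fed sessions. At group level, "we will use a factorial design with baseline versus 4-week contrasts to examine changes in brain activation"; the section then describes these changes as those "following oxytocin treatment in a-priori defined regions of interest". The list that follows gives VTA, OFC and anterior insula for the food-cue task, and dlPFC, dACC and preSMA for the stop-signal task. For mediation, "beta values will be extracted from subject-level contrast images for clusters within a-priori ROIs that meet family-wise error rate correction", at p < 0.05. The hypothalamus appears only at the end of the section: "Moreover, we will examine activation in the hypothalamus as a brain region responsible for energy homeostasis".

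Section 2.5.3 plans mediation through "key reward-related food motivation (VTA, OFC, anterior insula) and homeostatic (hypothalamus) regions" in the fasted and fed states, and through the three cognitive-control regions "during the fasted state from baseline following 4-week oxytocin treatment mediates change in caloric intake at a test meal 6 weeks from baseline". Aim 2 (Section 2.1) hypothesises that the reduction in caloric intake is "mediated by (a) reduced activation (in fasted and fed states) of reward-related food motivation (VTA, OFC, anterior insula) and homeostatic (hypothalamus) brain regions". The mediator panel of Figure 3 includes homeostatic regions, and Table 2 lists "Food cue task (fasting and post-meal): VTA, OFC, anterior insula, hypothalamus". Section 2.5.3 presents the mediation analyses as exploring mechanisms.

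**The concern.** Three gaps meet in one sentence of the plan.

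- **No fallback.** Section 2.5.3 commits to testing every listed region, but the mediator variable is defined only if a cluster survives. Multiple imputation (Section 2.5.3) cannot fill the gap, because the variable is then undefined for all participants rather than missing for some.
- **Hypothalamus.** It is a mediator in the aims and the mediation plan, but it is outside the list to which the extraction rule refers.
- **Unnamed term.** The thresholded effect could be treatment-by-time, time, within-oxytocin change or task activation. If it is treatment-related, the same participants choose the voxels and then supply the estimate of the treatment-to-mediator path.

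At stake is the reporting of Aim 2: which mediators receive an estimate and interval at all, and whether the reported sizes can be taken at face value.

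**Working it through.** **Inputs from the documents.** 25 evaluable per arm (Section 2.5.1); FWE p < 0.05 and the ROI list (Section 2.5.2); the mediator list (Section 2.5.3). The plan gives no figure for the mediation analyses. Its only computed figure, the primary power, reproduces: 3.2/(4 × √(2/25)) = 2.83, and Φ(2.83 − 1.96) = 0.81, against the stated 80%. This point does not depend on it.

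**Step 1, coverage of the rule.** Planned mediators: 4 food-cue regions × 2 states + 3 control regions × 1 state = 11. Covered by the Section 2.5.2 list: 3 × 2 + 3 = 9. The two left out are the hypothalamus, fasted and fed.

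**Step 2, simplest illustration of selection.** Assume one value per region, selected on the between-arm change at two-sided p < 0.05 with no voxel search. The standard error is √(2/25) = 0.283 SD, so an observed difference of about 2.01 × 0.283 = 0.57 SD is needed to pass.

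| True effect (SD) | P(pass) | Expected with a value, of 9 | Mean effect if passed | Ratio to truth |
|---|---|---|---|---|
| 0.2 | 0.11 | 1.0 | 0.63 | 3.2 |
| 0.35 | 0.23 | 2.1 | 0.71 | 2.0 |
| 0.5 | 0.41 | 3.7 | 0.76 | 1.5 |
| 0.8 | 0.79 | 7.1 | 0.90 | 1.1 |

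Even at 0.8 SD, all nine have a value with probability 0.791⁹ = 0.12 if regions are independent.

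**Step 3, voxel search, treatment-related term.** Assumed, not from the documents: a 600-voxel ROI of 2 mm voxels, 6 mm smoothness, half the between-subject variance shared across the ROI, a uniform effect, a mediator-to-outcome slope of 0.3, and voxel-level FWE. The simulated threshold is |t| = 3.71, so a surviving voxel must show about 3.71 × 0.283 = 1.05 sample SD whatever the truth. Results for true effects of 0.3 / 0.5 / 0.8 SD:

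- No cluster: 77 / 45 / 9% of trials. A separately coded run of the same 25-per-arm, 600-voxel case gave 73 / 39 / 4%.
- Extracted effect where a cluster survives: 0.99 / 1.02 / 1.10 SD (separate run 0.97 / 1.00 / 1.08).
- Nominal 95% interval for that path covers the truth in 0 / 18 / 90% of trials with a cluster.
- Indirect effect: 0.22 / 0.24 / 0.30, against a true 0.3 × effect = 0.09 / 0.15 / 0.24. Its interval is wide and still covers in 90 / 93 / 95%.
- No true effect: a cluster in 4.9% of trials and joint mediation in 0.9% (mask mean 1.5%).

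**Step 4, sensitivity.** With cluster-level FWE and cluster-forming p < 0.001, the extracted effect is 0.93 / 0.97 / 1.03 SD, path coverage 0 / 41 / 96% and no cluster 77 / 42 / 8%. With forming p < 0.005, the figures are 0.84 / 0.87 / 0.96 SD, 0 / 80 / 97% and 71 / 37 / 7%. With voxel-level FWE, over ROI sizes of 100 to 3000 voxels and shared variance of 25 to 75%, a true 0.5 SD is extracted as 0.92 to 1.10 SD. Over all these variants the overstatement at 0.5 SD runs from 0.87/0.5 = 1.7 to 1.10/0.5 = 2.2 times.

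**Step 5, time effect pooled over arms.** With placebo unchanged, extraction gives 0.33 / 0.49 / 0.79 SD, so there is no material inflation. The cluster search, however, sees only half of an effect confined to oxytocin: no cluster in 76 / 44 / 8%, and the treatment-to-mediator path is significant in 8 / 35 / 86% of all trials, against 28 / 65 / 96% for a whole-ROI mean. If placebo also changes by 0.3 SD, there is no cluster in 4 / 0 / 0% and no power loss.

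**The case against.** The strongest reply has four parts.

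- **The contrast is not wholly unnamed, and the hypothalamus is not unplanned.** The subject-level contrasts and the baseline-versus-week-4 factorial model are stated; only the group-level term is missing. The hypothalamus is pre-specified in three other places, and the phrase for a-priori ROIs could be read to include it. This stands: the fault is an inconsistency between sections plus a missing rule, and the count of 9 of 11 requires the list to be exhaustive.
- **The inflation is conditional.** A reader might infer that the plan is circular and its mediation estimates are therefore biased. The documents do not establish that, because under a pooled term the bias does not arise. The size also depends on voxel- or cluster-level FWE: the 18% path coverage at 0.5 SD becomes 41 or 80% in the cluster-level runs. The direction and the no-cluster rates persist.
- **Inferential harm is small.** Indirect-effect coverage stays at 90 to 95%, and detection under the treatment-related rule is 23 / 55 / 91%, against 28 / 63 / 95% for a mask with fallback. This stands.
- **A mask can do worse.** The uniform effect favours a mask mean. For 0.8 SD confined to 64 of 600 voxels, the FWE search finds it in 68% of trials, a 144-voxel mask around it has 34% power, a whole-ROI mean 7%, and a mask that misses it 5%. This stands, and it is why the cluster search should be kept.

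Exploratory status lowers the stakes, but it does not supply a value for a planned mediator that has none.

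**Conclusion.** The point holds in a limited form. Two defects follow from the text alone: there is no mediator value or fallback where no cluster survives, and the hypothalamus is a planned mediator outside the ROI list. The third is conditional. If the thresholded term is treatment-related, point estimates of the path and of the indirect effect are overstated where a cluster survives. For a true 0.5 SD effect, the extracted path is about 1.0 SD (0.87 to 1.10 over the variants run) and the indirect effect 0.24 against 0.15. These sizes rest on assumed ROI size, effect shape, shared variance and outcome slope.

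Three stronger readings are not supported. False mediation findings are not raised (0.9% per region in the simulation). The primary, key secondary and safety analyses do not use these values. The plan nowhere says that absence of a cluster will be reported as absence of mediation; that is only a reading the missing rule leaves open. The change is worth making, but it concerns exploratory analyses only.

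**What to change.** Before unblinding, amend Sections 2.5.2 and 2.5.3 as follows.

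1. Name the group-level term that defines clusters, and say whether FWE correction is voxel- or cluster-level.
2. Add the hypothalamus to the ROI list.
3. For mediation, extract the mean beta from one pre-specified, treatment-independent mask per region and session for all seven regions. The mask can be anatomical or based on the arm-blind baseline task contrast. Report all 11 mediators with intervals whether or not a cluster survives. If a task mask is used, state its threshold and an anatomical fallback; p < 0.001 with at least 10 voxels is only an example.
4. State a multiplicity approach, or label the 11 analyses explicitly as exploratory. At 1.5% each, and if independent, the chance of at least one false mediation is 1 − 0.985¹¹ = 15%.
5. Keep mediation on the FWE clusters alongside, labelled as subject to selection.

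The cost is plan wording and some analysis code, with no new data. The downside is lower power of the mask mean for a focal effect, which the retained cluster search offsets. Where the task activates a region weakly, the fallback would be used often: in simulation, in 0.3 / 41 / 98% of trials for task effects of 0.6 / 0.3 / 0 SD.

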2.5.3. Statistical analysis plan

Figure 3 shows our statistical analysis plan. We will perform statistical analyses using R statistical software, and appropriate R packages [54]. For continuous endpoints (see 2.3.), we will apply mixed model regression for repeated measurements (MMRM). We will consider the between-group (oxytocin versus placebo) difference in the least-squares mean change of each individual endpoint variable from baseline to each follow-up study time point of interest as the response in MMRM; the change from baseline to week 8 study time point (end of treatment) will be of primary interest (see 2.3.). Treatment group (oxytocin versus placebo), study time point (visit), and treatment group*study time point interaction will be included as fixed factors in MMRM. The baseline value of the endpoint variable and stratification factors (biological sex, BMI) will be entered as covariates. Additional covariates may be considered as appropriate. The intercept and time slope of individual participants will constitute random effects. Parameters of MMRM will be estimated via restricted maximum likelihood (REML). Depending on the distributional characteristics of the data, we may apply logarithmic transformations and/or robust statistical methods. We will adjust for multiple comparisons where appropriate via the approach of Hothorn, Bretz, and Westfall based on single-step simultaneous inference using a joint multivariate t-distribution [55]. We will use a modified intention-to-treat approach for efficacy analyses, including all randomized participants with available data for at least the second baseline visit

(randomization/initiation of treatment) and the first on-treatment study time point. We will apply a per-protocol approach for sensitivity analysis, including only randomized participants who complete the study and demonstrate $\geq 80\%$ adherence to treatment. We will carefully examine patterns of any missing data regarding their relationships with the outcomes of interest and incorporate uncertainty due to missing data with multiple imputations where applicable.

We will conduct regression-based mediation analyses to explore mechanisms underlying the proposed effects of intranasal oxytocin treatment: We will investigate whether (a) the change in brain activation in key reward-related food motivation (VTA, OFC, anterior insula) and homeostatic (hypothalamus) regions during fasted and fed states as well as in cognitive control-related regions (dlPFC, dACC, preSMA) during the fasted state from baseline following 4-week oxytocin treatment mediates change in caloric intake at a test meal 6 weeks from baseline, (b) the change in caloric intake at 6 weeks from baseline mediates the percentage change in body weight at 8 weeks from baseline, and (c) the change in REE at 6 weeks from baseline mediates the percentage change in body weight at 8 weeks from baseline.

Safety and compliance endpoints (assessed at each study time point) will be reported and tested for between-group (oxytocin versus placebo) differences. Endpoints regarding the off-treatment follow-up study time point (week 14 visit) will be reported and analyzed using MMRM in relation to baseline and end of treatment (week 8 visit) time points where appropriate (separately from on-treatment analyses).

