2.2. Study design, participants, and randomization

We are conducting a randomized, double-blind, placebo-controlled study to investigate the effects of intranasal oxytocin (24 IU, 4 times/day, for 8 weeks) in adults with obesity (BMI ≥ 30 kg/m²), aged 18–45 years. We randomized 61 individuals to achieve our target evaluable population of at least 50 participants who complete the 8-week treatment period. Participants were stratified by

biological sex (female/male) and obesity class (class 1: BMI 30.0–34.9 kg/m², class 2: BMI 35.0–39.9 kg/m², class 3: BMI ≥40.0 kg/m²) and randomized 1:1 to receive oxytocin or placebo. The unblinded study pharmacist performed randomization. All other study staff and participants are blinded to treatment assignment. We recruited participants through Massachusetts General Hospital (MGH) and advertisements online/in the surrounding community. Table 1 summarizes the inclusion and exclusion criteria of the study.

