2.4. Study procedures and assessments

Study time points comprise the screening visit to determine eligibility, two baseline visits (the second one includes randomization and treatment initiation after baseline assessments are completed), on-treatment study time points (week 2, 4, 6, and 8 visits), and a final week 14 follow-up visit to assess sustained treatment effects and safety.

Study visits take place at the MGH Translational and Clinical Research Center and the Athinoula A. Martinos Center for Biomedical Imaging. We obtain and manage study data using a web-based secure Research Electronic Data Capture (REDCap) system [38].

See Figure 2 for an overview of the study design, including visits, endpoints, and assessment methods. Table 2 provides a detailed list of study procedures/assessments at each study visit.

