Intranasal oxytocin may reduce body weight via multiple complementary mechanisms. Oxytocin may suppress caloric intake via reduced activation of reward and homeostatic brain regions and increased activation of cognitive control brain regions. Oxytocin reduces inflammation, which in turn may reduce appetite and increase energy expenditure. Oxytocin increases thermogenesis and energy expenditure. These effects lead to lipolysis, fat oxidation, and reduced fat mass, ultimately resulting in weight loss.

[figure not shown]

Figure 2. Study design.

Abbreviations: IU, international unit; REE, resting energy expenditure; BL, baseline visit; W, week of visit.

Order of analyses

Randomized, double-blind, placebo-controlled clinical trial

Participants: F/M, 18-45 years, BMI ≥ 30 kg/m²

Randomization at BL: 1 : 1 oxytocin : placebo

Stratification: Biological sex, BMI

1 – Endpoints

Variable	Use/Objective	Variable type	Statistical model	Methods for missing data
Change(%) in body weight (Δ_{W8-BL})	Primary endpoint	Continuous	Mixed-model regression for repeated measurements (MMRM), adjustment for multiple comparisons as appropriate via approach of Hothorn, Bretz, and Westfall	Modified intention-to-treat approach (mITT), Multiple imputation (MI) where applicable
REE (adjusted for lean mass) (Δ_{W8-BL})	Key secondary endpoint	Continuous		
Total body, visceral, and liver fat mass (Δ_{W8-BL})	Key secondary endpoint	Continuous		
Caloric intake (Δ_{W6-BL} , Δ_{W8-BL})	Key secondary endpoint	Continuous		
Metabolic profile (Δ_{W8-BL})	Secondary endpoint	Continuous		
Psychological, behavioral and quality of life assessments	Secondary endpoint	Continuous	Descriptive statistics	
Vital signs, QTc on EKG, %IBW, BMI, waist-to-hip ratio	Vital signs, EKG, anthropometrics	Continuous		
Age, biological sex, race, ethnicity, coexisting conditions, medication	Demographic and clinical variables	Continuous/Categorical		

2 – Mediators

Mediator variable	Dependent variable	Independent variable	Statistical model
Brain activation (Δ_{W4-BL}): food reward, homeostatic and cognitive control regions	Caloric intake (Δ_{W6-BL})	Treatment (oxytocin vs. placebo)	Regression-based mediation analysis
Caloric intake (Δ_{W6-BL})	Change(%) in body weight (Δ_{W8-BL})	Treatment	
REE (Δ_{W6-BL})	Change(%) in body weight (Δ_{W8-BL})	Treatment	

3 – Safety and Compliance (all study time points)

Variable	Use/Objective	Variable type	Statistical model

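### The primary week-8 weight model fixes a restrictive within-participant covariance (random intercept and linear slope), which can misstate the week-8 standard error by a modest amount; an unstructured covariance should be pre-specified

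*Combined protocol and SAP*

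**What the plan says.** Section 2.5.3 calls the model for continuous endpoints an MMRM. For the mean it states that "treatment group*study time point interaction will be included as fixed factors in MMRM", alongside the main effects of treatment and visit, with the baseline value and the stratification factors as covariates. On timing, "the change from baseline to week 8 study time point (end of treatment) will be of primary interest". For dependence within a participant the only statement is "The intercept and time slope of individual participants will constitute random effects". Estimation is by REML. The section names no residual covariance, degrees-of-freedom method, sandwich standard error or alternative structure.

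Weight is measured on treatment at weeks 2, 4, 6 and 8 (section 2.4 and Table 2). Week 14 is analysed "separately from on-treatment analyses", so the slope spans the four on-treatment visits only.

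On attrition, section 2.2 says: "We randomized 61 individuals to achieve our target evaluable population of at least 50 participants who complete the 8-week treatment period". The modified intention-to-treat set in section 2.5.3 needs only the second baseline visit and the first on-treatment visit, so partial completers enter the model. Multiple imputation is mentioned conditionally and without detail. Robust methods are optional and tied to the distribution of the data.

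**The concern.** Because visit and its interaction with treatment are factors, the week-8 difference is a free parameter. The restriction is in the covariance. A random intercept, a random slope and an independent residual use 4 parameters, where an unrestricted covariance over four visits has 4 × 5 / 2 = 10. They force the variance to be a quadratic in time, with matching covariances.

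Week 8 is the last visit and carries the primary test. Its standard error comes from the fitted week-8 variance. If that variance is pulled away from the truth to fit a quadratic, the test runs above or below its nominal level. For participants who leave early, earlier visits inform the week-8 mean through the same covariance, so likelihood validity under missing-at-random dropout also depends on it. Nothing in the documents shows that individual weight change follows the assumed form, and the plan states no safeguard tied to the covariance.

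**Working it through.** **The plan's own figures.** Section 2.5.1 gives 25 per arm, SD about 4 kg, two-sided 0.05 and 80% power. The detectable difference is (1.960 + 0.842) × 4 × √(2/25) = 3.17 kg, or 3.23 kg with the t distribution; the plan says 3.2 kg. Power at 3.2 kg is 80.7% (normal) or 79.1% (t). The figure reproduces. It rests on a two-sample t-test, so this point does not touch it. Non-completion allowed by the target: (61 − 50)/61 = 18.0%.

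**The assumed form.** Var(t) = τ₀² + 2τ₀₁t + τ₁²t² + σ².

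**One case by hand, complete data.** Take the 4 kg SD as 4 percentage points at week 8 and assume independent increments, so the true variances at weeks 2, 4, 6 and 8 are 4, 8, 12 and 16. Code the visits x = −1.5, −0.5, 0.5, 1.5 (Σx² = 5) and write S for the true covariance, with trace 40.
- 1′S1 = 120, x′Sx = 34 and 1′Sx = 40.
- Residual variance: σ² = (40 − 120/4 − 34/5)/2 = 1.6.
- Intercept variance: 120/16 − 1.6/4 = 7.1. Slope variance: 34/25 − 1.6/5 = 1.04. Covariance: 40/20 = 2.
- Fitted week-8 variance: 7.1 + 2 × 2 × 1.5 + 1.04 × 1.5² + 1.6 = 17.04.
- Ratio to the truth: 17.04/16 = 1.065, so the standard error is √1.065 = 1.03 times what it should be.

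**Range over assumed covariances, complete data.** Over 18 assumed patterns the best-fitting planned structure gave a week-8 variance of 0.79 to 1.12 times the truth. The standard-error ratios are √0.79 = 0.89 and √1.12 = 1.06. With 45 degrees of freedom the critical value is 2.014. The actual level is then P(|t| > 2.014 × 0.89) = 8.0% at one end and P(|t| > 2.014 × 1.06) = 3.9% at the other. A second set of eight covariances gave ratios of 0.88 to 1.06 and levels of about 3.9% to 8.4%.

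**Simulation with dropout.** Assumed true week-8 effect −3.2, week-8 SD 3.7 to 4.0, and about 18% dropout after week 2, driven by the last observed value. Bias comes from N = 200,000 and standard-error ratios (model over empirical) from 600 trials of 61. Monte Carlo error is about 0.02 on bias and 3% on the ratios.

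| Assumed individual pattern | Bias, planned model, same direction in both arms | Bias, planned model, opposite directions | SE ratio, planned, no dropout | SE ratio, unstructured, no dropout |
|---|---|---|---|---|
| Linear | 0.00 | 0.00 | 0.98 | 0.98 |
| Independent increments | −0.03 | −0.11 | 1.05 | 1.02 |
| Plateau | −0.01 | −0.07 | 1.04 | 1.00 |
| Late divergence | +0.06 | +0.19 | 0.90 | 0.98 |
| Regain | −0.03 | −0.12 | 0.93 | 0.98 |

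With dropout and non-linear patterns, the planned model's standard-error ratio was 0.84 to 1.06 and its coverage 90% to 97%. Unstructured gave an absolute bias of at most 0.015, ratios of 0.94 to 1.03 and coverage of 93% to 96%.

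A separate simulation had 30 per arm, no true effect, 16% to 22% dropout in opposite directions by arm, and week-8 SDs of 3.2 to 4.5. Bias under the planned model was −0.21 (independent increments), −0.19 (plateau), +0.27 (late divergence) and −0.01 (SD growing linearly), about 0.2 of a standard error at most patterns. Across its settings, rejection at nominal 5% was 2.8% to 8.0% for the planned model and 3.8% to 5.3% for unstructured.

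**The case against.** The case for leaving the plan alone has real content.

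- **Linearity.** A reader might infer that the model forces each participant's visits onto a straight line. It does not: arm-by-visit means are free and there is residual error. Only deviations from the means are modelled as linear.
- **Bias.** A reader might also infer that dropout seriously biases the primary result. That needs non-linear deviations, dropout driven by outcome and opposite directions by arm, all together. With same-direction dropout the bias was at most 0.06 on an effect of 3.2, and 0.002 to 0.003 in a further large-sample check under no effect. The size in the opposite-direction case varies between simulations, so it is only a rough range.
- **Attrition.** The 18% is what the completer target leaves room for. Anyone lost before the first on-treatment visit is outside the analysis set, so dropout within the model may be lower.
- **Missing-data provisions.** The plan mentions multiple imputation, and no simulation included it. But it is unspecified, and it would not correct a standard error that is already wrong with complete data. The per-protocol analysis changes the population, not the covariance.
- **Parsimony.** Random intercept and slope is a recognised choice at this sample size, and the standard-error mistake is often conservative. That is fair, but the anti-conservative patterns cannot be excluded in advance. Unstructured behaved close to nominally in the simulations at this sample size.
- **The remedy's limits.** Unstructured does not remove all dependence on the covariance. With one covariance pooled over arms that truly differed (independent increments, SD 3, against late divergence, SD about 5) and same-direction dropout, both models were biased by −0.31.

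**Conclusion.** The point holds as a modest weakness that is cheap to cure; it does not invalidate the primary analysis. The standard error is the more material part, because it can be wrong in either direction without any missing data: about 12% too small to 6% too large, for a true level of about 4% to 8%. It vanishes if individual deviations are close to linear. Bias from missing-at-random dropout is secondary: about zero when dropout runs the same way in both arms, and about 0.1 to 0.3 percentage points for most non-linear patterns when it runs in opposite directions.

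These sizes rest on assumed trajectory shapes, an assumed dropout mechanism and timing, a 4 kg SD read as about 4 percentage points, and (in the simulation with an effect of 3.2) a week-2 value for all 61 participants. None of these is in the documents, so the figures show what is possible under the stated model, not what this trial will see.

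**What to change.** For percent change in body weight, state in section 2.5.3 and Figure 3, before unblinding:

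- an MMRM with visit (weeks 2, 4, 6, 8) as a categorical factor, treatment by visit, and the covariates already listed;
- an unstructured within-participant covariance with no random effects, fitted by REML;
- Kenward-Roger or Satterthwaite degrees of freedom;
- an ordered fallback if the model does not converge, for example heterogeneous Toeplitz and then heterogeneous AR(1);
- the random intercept and slope model as a sensitivity analysis.

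The cost is wording only. The price in the analysis is 10 covariance parameters instead of 4 from about 61 participants, slightly fewer effective degrees of freedom, and a small chance of needing the fallback. The covariance would still be pooled across arms, so the change reduces the dependence on it without wholly removing it.
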